6.4 SUBGROUPS

In general, model-based subgroup analyses will not be performed for this trial. Only summary statistics will be created based on these subgroups for adverse events as well as viral load data for the phase IIa part of the trial:

- Time from symptom onset to first drug intake (<3, \geq 3 days)
- Time from symptom onset to study randomisation (<3, \geq 3 days)
- Baseline severity of COVID-19 (mild, moderate)
- Age group (<65, \geq 65 years old)
- Gender (male, female)
- Serum or plasma antibodies against SARS-CoV-2 at baseline (present/absent)
- Baseline weight (<70, \geq 70 kg)

- Baseline BMI ($<35, \geq 35 \text{kg/m}^2$)
- COVID-19 symptoms at baseline (present/absent)
- Disease stage at baseline [based on WHO 11pt scale] (Score 1-3, Score 4)
- Viral load (nasopharyngeal swabs) at baseline ($<10^6, \geq 10^6 \text{ copies/ml}$)
- Trial site^[*]
- Viral variant^[*]

[*] These subgroups will only be considered if applicable (e.g. if more than one trial cite, if viral variant data available at data base lock for the CTR).

If there are subgroups with expression levels that contain less than 5 patients, the subgroup evaluation will be omitted (if there are two subgroups) or expression levels may be pooled based on medical judgement (e.g. pooling of the smallest trial sites until all are larger or equal than 5) or modified as deemed appropriate based on the characteristics of the included subjects.

6.5 POOLING OF CENTRES

This section is not applicable because centre is not included in the statistical model.

6.6 HANDLING OF MISSING DATA AND OUTLIERS

In general, missing data will not be imputed. Exceptions are detailed in the subsequent subsections.

6.6.1 Safety data

Missing or incomplete AE dates will be imputed in order to determine if an AE belongs into the on-treatment period (covering the treatment and residual effect period). Please see [Section 9.4](#) for an overview of the implemented procedures.

AEs with missing / incomplete onset dates are excluded from the time-to-event analyses (e.g. time to the onset of liver enzyme elevations). AEs with missing / incomplete onset or end dates are not included in the routine duration analyses (e.g. duration of an AE). If an AE is ongoing at the time of analysis, then the corresponding AE end date will be censored using the snapshot date and this AE will be included in the routine duration analysis if the onset date is complete.

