### 5.2. Assessments and Sample Collection

#### 5.2.1. Safety Assessments

##### Adverse Events

Adverse Events will be assessed by open questions or upon spontaneous reporting by the trial participants. All adverse events will be followed to resolution or until completion for the trial of the subject concerned. Serious Adverse Events (SAEs) will be collected during the entire study period for each individual trial subject until completion of the trial of the subject concerned (see also section 9.3). In the interest of participants' safety, follow-up for up to 30 days after the individual participant's study termination is required for SAEs that are not sufficiently resolved at the participant's final trial visit. The CTCAE (Common Terminology Criteria for Adverse Events) grading table (v5.0) will be used by trial investigators to report and grade Adverse Events. The development of Adverse Events will be followed until the day 90 visit (i.e., until the end of the trial).

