## 5.6. Follow-up Visits

Participants will be followed for a total of 90 days (+/- 7 days) after trial drug administration.

At these follow-up visits, trial staff will

- Review the interim medical history including concomitant medication
- Review safety laboratory results
- Perform symptom-directed physical exams
- Perform procedures and obtain samples as outlined in the Visit Schedule (**Appendix II**)

For SARS-CoV-2-infected individuals, trial visits may be conducted at home during the period of quarantine. Trial visits on days 5 and days 10 are considered optional for SARS-CoV-2-infected individuals in quarantine.

In healthy volunteers (**Groups 1A-1C**), an optional visit at day 5 may be included to facilitate denser PK sampling.

Should trial participants become hospitalized during the follow-up phase, the visit schedule should be followed as possible.

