### 5.7.1. Follow-Up after Withdrawal

In case of an early termination of a trial participant, the date and reason for early termination should be collected and reported to the Principal Investigator who will provide this information to the Sponsor and to the SMC. At the time of withdrawal and if the participant agrees, all procedures specified in the Final Study Visit according to the corresponding Visit Schedule (**Appendix II**) will be performed.

Any Adverse Event resulting in withdrawal of a participant will be followed up until resolution or until the adverse event is judged by the principal investigator or designee to have stabilized where possible.

Should a study participant become pregnant during the conduct of the clinical trial, separate informed consent for follow-up until delivery and for assessment of the newborn's health status or a report by the responsible pediatrician will be sought.

Participants who are withdrawn from the trial after DZIF-10c administration will not be replaced, except for participants during the dose-escalation phase of the trial that are not followed until at least the day 7 visit after inhalation for reasons not related to safety events.

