## 9.2. Documentation and Follow-Up of Adverse Events

### 9.2.1. Documentation of Adverse Events and Adverse Drug Reactions

The occurrence of (S)AEs and ADRs will be documented starting with the provision of informed consent and until the termination of the clinical trial for the individual participant using the applicable case report form (CRF).

All adverse events, regardless of whether a causal relationship between the AE and study drug is suspected, will be followed-up until the associated symptoms have subsided, abnormal laboratory results have returned to pre-event levels, or the study has been completed or terminated for the individual participant.

Persistent AEs that do not resolve between individual visits will be recorded once. The initial severity will be documented at the time the event is first reported, and the highest severity will be documented should the persistent AE become more severe.

Should an AE become serious within the reporting period, it should be reported to the sponsor immediately (i.e., no more than 24 hours after learning that the event became serious) by using the trial-specific SAE form. Additionally, as soon as a documented Adverse Event becomes serious, the SAE information should be amended on the AE eCRF page by providing the date that the event became serious as onset date of the SAE and completing all data fields related to serious adverse event.

Documentation of AEs includes

- Description of AE
- Date and time of onset and resolution
- Grading/Severity
- Relationship to study drug
- Seriousness
- Effect on the trial drug administration schedule
- Need for treatment and action taken
- Outcome
- Written summary / narrative (for SAEs, AESIs, and DLTs)

Pre-existing diseases (i.e., medical conditions starting before study drug administration) are not documented as AEs but as medical history. However, worsening of pre-existing diseases will be documented as AEs.

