### **9.3. Reporting of Serious Adverse Events, Adverse Events of Special Interest, Dose-Limiting Toxicities, Pregnancy and Changes in Risk-Benefit Assessment**

Every SAE that occurs from the provision of informed consent to participate in the trial until the trial participant's last study visit must be documented on the appropriate CRF and in addition be reported on a SAE form to the sponsor. In the interest of participants' safety, follow-up for up to 30 days after the individual participant's study termination is required for SAEs that are not sufficiently resolved at the participant's final trial visit.

Adverse Events of Special Interest (AESIs) and Dose-Limiting Toxicities (DLTs) should be reported to the sponsor within 24 h of the site becoming aware of the event.

Pregnancies must be documented on a separate pregnancy form and reported to the sponsor within the defined periods (see Section 9.3.2.).

An Investigator Handout providing detailed information of reporting procedures will be provided to the trial sites.

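### SAP 6.6.1 censors ongoing AEs at the trial-wide snapshot date rather than at the participant's last AE assessment, so AE durations can include time nobody observed (minor)

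*SAP*

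**What the plan says.** SAP 6.6.1 leaves AEs with missing or incomplete onset or end dates out of the routine duration analyses, with one exception. If an AE is ongoing when the analysis is done and its onset date is complete, "then the corresponding AE end date will be censored using the snapshot date and this AE will be included in the routine duration analysis". The test is whether the AE is ongoing, not whether the participant is still under observation. There is no cap at a participant-level date.

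The protocol ends AE follow-up participant by participant:

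- Protocol 5.2.1: "All adverse events will be followed to resolution or until completion for the trial of the subject concerned", and "The development of Adverse Events will be followed until the day 90 visit".
- Protocol 9.2.1 lists the points at which AE follow-up stops. The last is when symptoms or laboratory values have not normalised "or the study has been completed or terminated for the individual participant".
- Protocol 5.6: "Participants will be followed for a total of 90 days (+/- 7 days) after trial drug administration".

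There are two extensions. For SAEs unresolved at the final visit, Protocol 9.3 (and 5.2.1) requires "follow-up for up to 30 days after the individual" participant leaves the study. Protocol 5.7.1 adds: "Any Adverse Event resulting in withdrawal of a participant will be followed up until resolution or until the adverse event is judged" to have stabilised, where possible.

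SAP 7.1 states that nobody will still be in the trial when the final analysis is done.

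**The concern.** The two documents use different clocks. AE observation stops at a date specific to each participant; the duration rule runs to a date common to all. An AE unresolved at the day 90 visit stays coded as ongoing, and its assigned length then grows with the time between that visit and the data snapshot. Two identical events get different durations only because the participants enrolled at different times.

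The SAP is stricter elsewhere. For time to symptom resolution (SAP 5.3.5, censoring rule 4), an unknown status is censored at the last consecutive diary entry. In SAP 5, censored AE dates are excluded when the date of last contact is derived, so the SAP itself does not treat such a date as evidence of contact.

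What is at stake is the meaning of any AE duration table. SAP 7 sets N, mean, SD, minimum, quartiles, median and maximum as the standard summary. In escalation groups of 3 to 6 participants, one or two unresolved AEs can dominate the mean, SD and maximum.

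**Working it through.** The documents give no figure for AE duration or for the gap between last visit and snapshot, so there is nothing to reproduce. The gap can be bounded from the time plan.

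**Inputs**

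- First patient first visit Q4 2020, last patient first visit Q2 2021, last patient last visit Q3 2021 (Protocol synopsis and Table 1, labelled tentative).
- Final visit at day 90, window ±7 days (Protocol 5.6, Appendix II).
- Interim 2 after 7 days of follow-up of the last phase IIa participant, plus 7 days of data cleaning (SAP 9.1.2).
- Assumptions: dosing falls on the first-visit date, and the earliest possible final snapshot is the last patient's last visit. All dates within the stated quarters are allowed if they are mutually consistent.

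**Final analysis, first participant**

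Unobserved time = last patient's last visit − first participant's last visit.

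| Case | First participant dosed | First participant's last visit | Last patient's last visit | Gap |
|---|---|---|---|---|
| Smallest, day 90 exactly | 31 Dec 2020 | 31 Mar 2021 | 1 Jul 2021 | 92 days |
| Mid-quarter dates | 15 Nov 2020 | 13 Feb 2021 | 15 Aug 2021 | 183 days |
| Largest, day 90 exactly | 1 Oct 2020 | 30 Dec 2020 | 28 Sep 2021 | 272 days |
| Smallest, with windows | 31 Dec 2020 | 7 Apr 2021 (day 97) | 1 Jul 2021 | 85 days |
| Largest, with windows | 1 Oct 2020 | 23 Dec 2020 (day 83) | 30 Sep 2021 | 281 days |

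These are minimum gaps, because the final snapshot cannot precede the last visit and its lag is not stated. For the last participant the gap is 0 days plus that lag. For an SAE followed the full extra 30 days, the first participant's range falls to 85 − 30 = 55 up to 281 − 30 = 251 days.

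**Effect on one event**

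Take an AE with onset on protocol day 3, unresolved at day 90, in the first participant.

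- Observed length: 90 − 3 + 1 = 88 days.
- Assigned under SAP 6.6.1: 88 + 92 = 180, 88 + 183 = 271, or 88 + 272 = 360 days.
- Ratio to observed time: 180/88 = 2.0, 271/88 = 3.1, 360/88 = 4.1.

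**Interim 2, first phase I participant**

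SAP 9.1.2.3 re-runs the escalation analyses at this point. With a snapshot at last dosing + 7 + 7 = 14 days, and using only the two first-visit quarters, the gap is 15 to 196 days at day 90 exactly, or 8 to 203 days with windows.

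From that snapshot to the last patient's day 90 visit is a further 90 − 14 = 76 days. An unresolved AE in a participant who had already finished therefore lengthens by at least about 76 days between the two reports, with no new observation.

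**The case against.** **The date is called censored.** This is true, and a censoring-aware summary could use it as such. But the SAP names no such method for AE duration, and SAP 7.8.1 describes the AE analyses as descriptive. Even a survival method would be censoring after observation had stopped.

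**The rule is meant for interims.** The wording about snapshots and ongoing events fits an interim, and for participants still being followed the gap is then only the time since their last visit. However, SAP 6.6.1 does not limit the rule to interims, and some phase I participants will have finished by interim 2.

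**No listed output uses AE duration.** This stands. It is not among the AE attributes in SAP 7.4.1, the displays in SAP 7.8.1, or the interim lists in SAP 9.1. The full output list is in a separate document that is not available here. If duration is tabulated, the median and quartiles would resist a few long values.

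**Some AEs are followed beyond the last visit.** This also stands, for unresolved SAEs and for AEs causing withdrawal. It narrows the set of affected events and shortens the gap for them.

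**Stronger readings the documents do not support**

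- *Durations are overstated two- to fourfold.* The ratios compare assigned with observed time. An AE unresolved at day 90 truly lasted longer than observed, by an unknown amount. What is shown is unobserved time being credited, not the size or direction of the error against the true duration.
- *The distortion runs by dose.* Dose levels do open in sequence, which makes this possible. But no group dosing dates are given, infected and uninfected groups can overlap, and two dose levels may enrol on one day (Protocol 4.1.1). Nothing indicates how many AEs would be unresolved in each group.
- *The randomised comparison is biased.* The three Group 2D arms are randomised 1:1:1 concurrently, so enrolment dates should balance in expectation.

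**Conclusion.** The rule as written is wrong for any participant whose AE follow-up has ended. At the final analysis that covers essentially every AE still coded as ongoing. The credited but unobserved time is at least 85 to 281 days for the first participant and falls towards the unstated snapshot lag for the last. These figures rest on the tentative quarters, dosing at the first visit, and a snapshot no earlier than the last patient's last visit.

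The consequence is minor. It is confined to descriptive AE duration summaries, and only to AEs unresolved at the participant's last assessment. The primary endpoint (participants with an AE within 7 days), DLT rules, PK, ADA and viral load do not use AE end dates.

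**What to change.** In SAP 6.6.1, replace the snapshot rule with wording such as: an AE ongoing at the time of analysis is censored at the earlier of the snapshot date and the participant's last AE assessment, and is flagged as ongoing. The last AE assessment is the last trial visit, or the later follow-up date for an unresolved SAE or an AE that led to withdrawal.

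Do not use the date of last contact in SAP 5. That is a known-alive date which includes vital status information, so it can fall after the last AE assessment.

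Then state the summary: Kaplan-Meier with these AEs censored, or durations of resolved AEs with the number ongoing alongside. Resolved-only durations favour short events, so that number must be shown with them. In groups of 3 to 6 participants, the second option with a listing is the practical choice.

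The cost is one sentence and one derived date in the SAP, made before the final database lock. Visit dates are already collected. The only check needed is that SAE and withdrawal-AE follow-up dates are recorded in the database.

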6.6.2 Pharmacokinetic data

Missing data will not be imputed.

6.7 BASELINE, TIME WINDOWS AND CALCULATED VISITS

As a general rule, the last assessment / measurement observed prior to start of trial medication will be assigned to baseline. Note that for some trial procedures (e.g., body weight, vital signs, laboratory tests) this may be the value measured on the same day trial medication was started. In these cases, it will be assumed that the measurements were taken prior to the intake of any study medication (if the measurement time was not captured). If no further data available, this can also be the last screening assessment. For viral load and pulmonary function test related

data it is paramount that the sample is taken prior to drug administration, and for these procedures time of sampling will be taken into consideration and compared to the time of drug intake.

Furthermore, for assessments of viral load data for the first 7 days after drug administration which require grouping to timepoints (e.g., descriptive statistics by timepoint, MMRM), the following will be done. Measurements for baseline (day 1) and days 2, 4, 6 and 8 will be included, where the measurement for day 6 is optional. The following time windows are allowed.

- The measurements for baseline and for day 2 must be taken exactly on the respective day. There is no time window.
- If there is no measurement on day 4, it will be replaced by a measurement on day 3 or day 5 with a preference for day 3.
- If there is no measurement on day 8, it will be replaced by a measurement on day 7.

If the optional measurement on day 6 is missing, it will be replaced by the value on day 5 or day 7 if these values have not been assigned to days 4 and 8, respectively. The measurement for day 5 will be preferred over day 7 if both values are available.

Additionally, for assessments of viral load data for the first 14 or 28 days after drug administration which require grouping to timepoints (e.g., MMRM), the following time windows apply. These analyses windows are non-overlapping and cover the whole trial period by using the middle between each scheduled visit.

- If there are no measurement on days 7 and 8, the day 8 measurement will be replaced by the earliest measurement up to day 11.
- If there is no measurement on day 15, it will be replaced by the closest measurement taken between day 12 and day 18.
- If there is no measurement on day 22, it will be replaced by the closest measurement taken between day 19 and day 25.
- If there is no measurement on day 29, it will be replaced by the closest measurement taken between day 26 and day 43.

Additionally for descriptive statistics, the following non-overlapping time windows apply.

- If there is no measurement on day 57, it will be replaced by the closest measurement taken between day 44 and day 74.
- If there is no measurement on day 91, it will be replaced by the closest measurement taken between day 75 and day 107.

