#### Screening Visit

At the screening visit, the Principal Investigator or subinvestigator will explain and discuss the aims and nature of the trial, potential risks, and the trial schedule with potential participants who will be provided the opportunity to address all questions and concerns they may have with study staff, relatives, and friends. Prior to the initiation of any study-related procedures, written informed consent will be obtained from each participant.

If the potential participant provides informed consent to participate in this trial, study staff will

- Obtain a complete medical history including the use of concomitant medication (including medication within the last 4 weeks prior to screening)
- Perform a general physical exam, including height, weight, vital signs (heart rate, blood pressure, body temperature, respiratory rate, and pulse oximetry), and examination of the skin and respiratory, cardiovascular, abdominal, and neurological systems
- Provide pregnancy counseling
- Determine the clinical score based on the WHO Clinical Progression Scale (**Groups 2A-2D**)

- Perform a pulmonary function test (**Groups 1A-1C**)
- Collect blood, urine, and swab samples for all tests indicated in the Visit Schedule (**Appendix II**)
  - At the screening visit, a single nasopharyngeal and/or oropharyngeal swab may be obtained to document absence or presence of SARS-CoV-2 infection. This swab is to be analyzed at the trial site's routine laboratory. An available SARS-CoV-2-RNA NAAT result documented in writing from a sample obtained within three days prior to trial drug administration is considered as an acceptable alternative. In all cases, nasopharyngeal and oropharyngeal swabs must be obtained at baseline prior to study drug administration in SARS-CoV-2-infected individuals.

Screening and Trial Drug Administration Visit Procedures may occur on the same day during the expansion phase of the trial (**Group 2D**).

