## 5.5. Trial Drug Adminstration Visit

Prior to the study drug administration, trial staff will

- Review the informed consent form
- Discuss the planned procedure and any potential questions with the participant
- Review the interim medical history including concomitant medication
- Review screening laboratory results including safety laboratory parameters
- Review eligibility criteria
- Perform a symptom-directed physical exam
- Perform procedures and obtain samples as outlined in the Visit Schedule (**Appendix II**)
- Obtain a baseline PK serum sample
- Perform baseline assessments of vital signs
- Perform the randomization procedure (**Group 2D only**)

- Perform a pulmonary function test (**Groups 1A-1C** only)

If the screening visit of healthy volunteers (**Groups 1A-1C**) occurred >3 calendar days prior to the start of the antibody administration, the negative NAAT result of an additional naso- or oropharyngeal swab obtained within (inclusive) 3 calendar days of the antibody inhalation must be available prior to the start of the drug administration (e.g., rapid PCR from swab obtained on the day of inhalation).

DZIF-10c or placebo will be prepared by the local pharmacy and administered as described in Section 5.9.

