## Outcomes and Target Variables

### Laboratory Parameters, Vital Signs, Symptoms

Changes in safety laboratory parameters, vital signs and symptoms will be summarized descriptively. Changes in laboratory parameters and vital signs will additionally be calculated relative to the results obtained at baseline (day 0 prior to study drug administration).

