## Appendix II Visit Schedule

Appendix II A - Visit Schedule - Groups 1A-1C - **HEALTHY PARTICIPANTS**

Version: V04\_0 01-APR-2021

Visit	1	2	3	4	5	6	7	8	9	10	11
Study Week	Screen	Wk 0				Wk 1	Wk 2	Wk 3	Wk 4	Wk 8	Wk 13
Study Day	D-7 to D-1	D 0	D 1	D 3	D 5 	D 7	D 14	D 21	D 28	D 56	D 90
Visit Window (+/- days)	-	-	-	1	1	1	2	3	3	4	7
Eligibility and History											
Informed Consent	x										
Inclusion/Exclusion criteria	x										
Demographics	x										
Medical History	x	x	x	x	x	x	x	x	x	x	x
Concomitant Medication	x	x	x	x	x	x	x	x	x	x	x
Study Intervention											
In-Patient Admission		x									
DZIF-10c Inhalation		x									
Study Procedure											
ECG	x										
AESI / Inhalation-related reactions	x	x	x	x	x	x					
Adverse Events	x	x	x	x	x	x	x	x	x	x	x
General Physical	x										
Directed Physical 	x	x	x	x	x	x	x	x	x	x	x
Vital Signs 	x	x 	x	x	x	x	x	x	x	x	x
Weight	x								x		x
Height	x										
Pregnancy counseling	x										
Pregnancy testing in women of childbearing potential	x	x 					x		x	x	x
Pulmonary function testing	x	x 	x			x			x		x
Biosamples											
Virology screening labs  (Local lab)	x										
Safety lab  (Local lab)	x	x	x	x	x	x	x		x	x	x
Coagulation parameters (INR, PTT) (Local lab)	x										
Urinalysis 	x					x			x		x
SARS-CoV-2 antibody serology  (Local lab)	x	x									
PK samples (Central lab)		x 	x	x	x	x	x	x	x	x	x
Naso- or Oropharyngeal SARS-CoV-2 swab (Local lab) 	x	x 				x					
Anti-DZIF-10c antibody (ADA) assay sample (Central lab)		x					x		x	x	x
Research lab (PBMCs) (Central lab)		x							x		x

1. Optional visit.

2. Symptom-oriented examination.

3. Vital signs: Heart rate, systolic/diastolic blood pressure, temperature, respiratory rate, SpO2 (pulse oximetry).

4. Vital signs determined prior to inhalation, at the end of the inhalation, 1 h (+/- 10 min) post end of inhalation, and 4 h (+/- 15 min) post end of inhalation.

5. Negative serum or dipstick urine b-HCG from sample obtained on day of infusion must be available prior to the start of the administration.

6. Pulmonary function testing to be performed prior to inhalation, 30 min (+/- 5 min) post end of inhalation, and 4 h (+/- 15 min post end of inhalation).

Parameters: FEV1, FVC, FEV1/FVC, VC, IVC, PEF, PIF.

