7.8.3 Vital signs

Only descriptive summary statistics will be presented for observed values and change from baseline by treatment and visit. The frequency of subjects with marked changes in vital signs

will also be summarised by treatment according to the parameters defined in [Section 5.4.5](#) of this document.

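### SAP 6.7 assumes an untimed dosing-day vital sign is pre-dose, although only 1 of 4 (escalation) or 1 of 6 (Group 2D) scheduled readings is

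*SAP*

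**What the plan says.** SAP 6.7 sets baseline as the last value before the start of trial medication. It then names body weight, vital signs and laboratory tests as examples where this may be a value from the dosing day, and says of them that "it will be assumed that the measurements were taken prior to the intake of any study medication (if the measurement time was not captured". If nothing else is available, the last screening value may serve. Viral load and pulmonary function are treated differently: "for these procedures time of sampling will be taken into consideration and compared to the time of drug intake".

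Protocol 8.1.4 says that changes in laboratory parameters and vital signs are "calculated relative to the results obtained at baseline (day 0 prior to study drug administration". Protocol 5.5 includes "Perform baseline assessments of vital signs" among the steps before dosing.

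The readings continue after dosing. For Groups 1A-1C, footnote 4 of Appendix II A has "Vital signs determined prior to inhalation, at the end of the inhalation, 1 h (+/- 10 min) post end of inhalation", and then a 4 h reading. Footnote 7 of Appendix II B repeats this for Groups 2A-2C. For Group 2D it lists readings before inhalation, at the end of inhalation, 15 minutes into the infusion, at the end of the infusion, and 1 h and 2 h later.

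The baseline is used in SAP 7.8.3: "Only descriptive summary statistics will be presented for observed values and change from baseline by treatment and visit". The same section counts participants with marked changes as defined in SAP 5.4.5, where each definition combines an absolute limit with a change from baseline.

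**The concern.** The fallback suits a procedure done once on the dosing day, because an untimed value can then reasonably be taken as the pre-dose one. It does not suit a procedure that the protocol deliberately repeats after dosing. Of the three procedures SAP 6.7 names, only vital signs are in that position. Weight is scheduled at screening, day 28 and day 90 (protocol day numbering). Safety laboratory tests appear once on day 0, with no scheduled post-dose repeat.

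The SAP recognises the problem for pulmonary function, which is also measured before and after dosing, and guards against it there. It gives no reason for leaving vital signs out.

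At stake is the meaning of change from baseline in a trial whose primary objective is safety and tolerability, and whose protocol expects inhalation and infusion reactions typically within the first hour. If a reading taken during or after a reaction becomes the baseline, the change caused by the reaction is partly or wholly removed from that participant's results.

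**Working it through.** The SAP gives no figure to reproduce. The check is a count of scheduled dosing-day readings, followed by applying the rule to them.

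**Inputs.** Vital signs: Protocol Appendix II A footnote 4 and Appendix II B footnote 7. Pulmonary function: Appendix II A footnote 6 ("Pulmonary function testing to be performed prior to inhalation, 30 min (+/- 5 min) post end of inhalation, and 4 h"). Same-day screening: Protocol 5.4 ("Screening and Trial Drug Administration Visit Procedures may occur on the same day during the expansion phase of the trial").

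**Step 1: count.** Share pre-dose = readings before inhalation / all scheduled dosing-day readings.

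| Procedure and group | Pre-dose | After start of study drug | Share pre-dose | Time check in SAP 6.7 |
|---|---|---|---|---|
| Vital signs, 1A-1C and 2A-2C | 1 | 3 | 1/4 = 25% | No |
| Vital signs, 2D | 1 | 5 | 1/6 = 16.7% | No |
| Vital signs, 2D, screened the same day | 2 | 5 | 2/7 = 28.6% | No |
| Pulmonary function, 1A-1C | 1 | 2 | 1/3 = 33.3% | Yes |

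The observation table in Protocol 5.5 independently lists 3 post-dose vital-sign readings for the escalation groups and 5 for Group 2D, which agrees.

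**Step 2: apply the rule.** Suppose one post-dose reading has no recorded time. SAP 6.7 assumes it is pre-dose, so it becomes a candidate for baseline alongside the true pre-inhalation reading. The general rule then takes the last candidate. The SAP does not say how an untimed reading is ordered against a timed one, or that the scheduled pre-inhalation reading takes precedence. Nothing in the text therefore prevents the post-dose value from being selected. That outcome contradicts Protocol 8.1.4.

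**Step 3: consequence for one participant** (invented values, for illustration only). Systolic pressure is 112 mmHg before dosing and 98 mmHg after. SAP 5.4.5 defines a marked decrease as below 100 mmHg with a fall of more than 10 mmHg.

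- Correct baseline of 112: the fall is 112 - 98 = 14 mmHg, and 98 is below 100, so it is flagged.
- Baseline taken as 98: the fall is 98 - 98 = 0 mmHg, so it is not flagged.

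**Step 4: what is not touched.** The primary endpoint in SAP 5.1 and 7.4.1 is the proportion of participants with any adverse event within 7 days. It uses no vital-sign baseline.

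**The case against.** The strongest reply is that the sentence is only a fallback. The governing rule still asks for a value before trial medication, and the fallback speaks of a single same-day value. Its natural purpose is to keep a genuine pre-dose reading whose clock time was not written down. Dosing-day readings are also defined by nominal time point, and if the eCRF carries those labels a programmer can pick out the pre-inhalation reading without a time. Read with Protocol 8.1.4, and with no change to the vital-sign baseline declared in SAP 4.2, the intention is plainly a pre-dose baseline.

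Much of this stands. The rule matters only when a time is missing, and labels may settle even those cases. The eCRF is not available, so neither can be confirmed. What remains is that SAP 6.7 decides by recorded time alone, does not mention labels, and states the assumption without excluding repeated readings. An intention that must be inferred from another document is weaker than one clause in the rule itself.

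A reader might go further in three ways that the documents do not support:

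- **That 75% or 83% of vital-sign baselines will be wrong.** The counts describe the schedule. They are not error rates.
- **That the safety conclusions are compromised.** The primary endpoint does not use this baseline. Individual reactions are still captured by the 1 h reaction check (Protocol 5.5), adverse-event records with onset times (Protocol 9.2.1) and participant listings (Protocol 8.1.2).
- **That SAP 7.8.3 is deficient because it summarises by treatment and visit.** That wording does not exclude time-point rows within a visit. The separate table-of-contents document for the interim outputs may already include them. Protocol 8.1.4 promises only descriptive summaries and change from baseline for vital signs, so no commitment is broken.

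**Conclusion.** The point holds as a minor defect in a stated rule. SAP 6.7 extends to vital signs an assumption that fits only procedures without post-dose repeats on the dosing day, and it withholds from them the time check given to pulmonary function. If a time is missing, the rule can admit a post-dose baseline, against Protocol 8.1.4.

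Its size is limited. The 1 of 4 and 1 of 6 shares (2 of 7 with same-day screening) show why the assumption is unsafe, not how often it fails. The number of wrong baselines is unknown and may be zero. Only the vital-sign change-from-baseline and marked-change summaries could be affected.

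The conclusion rests on two assumptions: that at least one dosing-day reading could reach the database untimed, a case SAP 6.7 itself provides for, and that the rule is programmed as written, without time-point labels. If every reading carries a usable time or label, the correction changes no result.

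**What to change.** In SAP 6.7, remove vital signs from the procedures assumed to be pre-dose, and state:

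- Vital-sign baseline is the scheduled pre-inhalation reading.
- If that is missing, use the last reading timed before the start of inhalation.
- If there is none, use the screening reading.
- A dosing-day reading with neither a time nor a time-point label is listed but not used as baseline.

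The cost is a few lines of text and a small change to the baseline derivation. No new data are needed, because Protocol 5.5 already requires the pre-dose reading.

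Optionally, and outside the finding, SAP 7.8.3 could add a descriptive dosing-day table of the six vital signs by treatment and scheduled time point. For Group 2D that is 6 time points x 6 parameters x 3 arms = 108 summaries, and for the escalation phase 4 x 6 x 6 groups = 144.
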